8.1 Patient Selection

Patients with AML in first remission (CR or CRi) and who otherwise meet the inclusion/exclusion criteria will be recruited for enrollment into the study. Patients will be advised of the clinical protocol by the Investigator. If the patient is interested and is potentially eligible for participation in the study, he/she will be provided with the ICF to review and sign. The ICF includes a detailed explanation of the study design and the potential risks and benefits of treatment. Patients who agree to participate in the study will be provided with a copy of the signed consent form; the original signed consent document will be filed in the patient's medical record. Only eligible and consenting patients will be entered into the study.

Patients will be screened by the site's Investigator or study nurse/coordinator prior to study entry. All patients enrolled on the study will be entered into a patient registration log at each site. Each screened patient will be assigned a sequential patient/study screening number with digits indicating site number and patient study number (e.g., XX-YYY, where XX denotes site number and YYY denotes patient study number as assigned at screening). Original screening records and source documents should be kept for all patients, including those who fail to meet

the patient eligibility requirements and any completed eCRFs should be retained for monitoring and auditing. Each patient's data obtained from subsequent evaluations should be recorded and evaluated in the source documents and eCRF. Prior to treatment, the Investigator will re-confirm patient eligibility criteria and assignment of the correct patient study number.

8.2 Medical History

Medical history includes current and past medical conditions and smoking history, date of AML diagnosis, prior AML treatment, response to prior treatment, and date of relapse, if applicable. Information concerning any prior malignant diagnoses with particular focus on cytotoxic therapies received for prior malignancies (i.e., dates/duration of anthracycline for prior breast cancer) is to be collected whenever feasible.

8.3 Prior and Concomitant Medication

Medications taken within 28 days prior to screening and throughout the study are to be collected and recorded.

8.4 ECOG Performance Status

See Section [15.2](#) for a scoring guide.

8.5 Physical Examination

Physical examination includes evaluation by body system and height (at screening only).

8.6 Vital Signs

Vital signs include temperature, heart rate, respiration rate, pulse oximetry, and BP. Collection should occur after the patient has been sitting for 3-5 minutes.

8.7 Electrocardiograms

All patients will have a 12-lead ECG performed at the screening visit and pre-treatment visit (Study Day 0 or 1), as well as on Day 28 (\pm 3 days, and Day 35 [\pm 3 days] only if delayed end of cycle) of each cycle. During the days when patients are undergoing PK sampling (Cycles 1 and 3, infusions 1 and 5), an ECG will be performed at 3 distinct time points (triplicates) within 5 minutes prior to each PK sample collection pre-infusion and at 30 and 60 minutes post-infusion (see [Table 7](#)). An ECG should be performed after patient is supine for 5 minutes. All ECGs will be analyzed locally.

8.8 Clinical Laboratory Tests

The following assessments should be done per the visit schedule and processed by the local laboratory.

- Hematology: Minimally, scheduled hematology collections should include white blood cell (WBC) count, differential white cell count (lymphocytes, monocytes, basophils, eosinophils, and neutrophils), red blood cell (RBC) count, hematocrit, hemoglobin and platelet count.

- Serum albumin: May be a component of the serum chemistry panel. See Section [7.5.5.1.3](#) for administration of albumin if serum albumin decreases to <3.0 g/dL in the immediate post-treatment period.
- Serum electrolytes and chemistry: Sodium, potassium, bicarbonate, chloride, BUN, creatinine, glucose, ALT, albumin, alkaline phosphatase (ALP), AST, bilirubin (total, direct, and indirect), calcium, creatine phosphokinase (CPK), magnesium, LDH, phosphate, total protein, and uric acid.
- Coagulation parameters: PT and/or INR and aPTT.
- Urinalysis: Appearance, color, pH, specific gravity, ketones, leukocytes, protein, glucose, bilirubin, urobilinogen, and occult blood.

8.9 Urine or Serum Pregnancy Test

A urine or serum pregnancy test will be performed within 1 week prior to treatment for WOCBP who are not on acceptable birth control measures. The pregnancy test should be performed at the clinical research site and processed by the local laboratory.

8.10 Vision Assessment

All patients will be questioned regarding any changes in visual acuity and/or color vision. Patients who have experienced any \geq Grade 2 study drug-related changes in vision (CTCAE v4.03 Grade) will have an ophthalmologic consultation and/or examination performed. In the event any abnormalities are detected, the patient will be followed up as per the recommendations of the consulting ophthalmologist. Management of treatment-related ocular disorders with inflammatory characteristics should include corticosteroid eye drops and/or other measures, as indicated by an ophthalmologist. In the setting of persistent study drug-related ocular disorders \geq Grade 2, consultation with the study's Medical Monitor is required.

8.11 Tumor Assessments

Following determination of eligibility, locally, the following assessments must be performed centrally at baseline (after local determination of eligibility, but prior to receiving investigational treatment on study) within 14 days prior to the first administration of SL-401, and on the following schedules until, in the judgment of the Investigator, there is evidence of relapsed or progressive disease.

8.11.1 Bone Marrow and Peripheral Blood Examinations including Biological/Target/Correlative Studies by Central Laboratory

Bone marrow aspirates (+ biopsy) will be collected within 14 days prior to first administration of SL-401 and 28 (\pm 7) days after the start of Cycles 2, 4 and 6, every 3 months (\pm 1 month) thereafter through 12 months after start of SL-401, and thereafter at the discretion of the Investigator. If the Cycle 2 (Day 28 (\pm 7 day) bone marrow examination is empty (i.e., hypocellular) or inadequate, a bone marrow examination should be repeated in 14 (\pm 7) days to document response. If additional time is required to complete the repeat examination,

consult with the Medical Monitor. The Cycle 2, 4 or 6, Day 28 (\pm 7 days) bone marrow assessment should occur on Day 28 (\pm 7 days) even in the setting of patients receiving SL-401 over 6-10 days (as opposed to 5 consecutive days).

For adequate MRD assessment, it is critical that the first aspirate from each bone marrow collection: 1) consists of 2 mL of BM aspirate in its entirety; and 2) be shipped in its entirety via priority overnight to the central processing laboratory ([REDACTED], Attn: [REDACTED] [REDACTED]), as described in the Laboratory Manual. Additional bone marrow may be used for local assessment at the Investigator's discretion.

Results of bone marrow examinations will be provided to the Investigator by the central laboratory within 1 week of sample receipt.

8.12 Pharmacokinetic Studies

An intensive schedule for collection of blood samples after specific infusions during Cycles 1 and 3 of SL-401 will be used to determine plasma concentrations of SL-401. The concentration of SL-401 in plasma samples will be determined by a sensitive and specific sandwich enzyme-linked immunosorbent assay (ELISA) method at a contract laboratory according to industry GLP bioanalytical practices. Plasma concentration data over time will be used to characterize the PK disposition of SL-401, to assess any change in the PK properties of SL-401 during the 5-day course of treatment or between cycles of treatment, and relate the PK characteristics of SL-401 to immunogenicity, toxicity, and disease activity.

Collectively, the SL-401 plasma concentration-time data will be analysed by conventional non-compartmental PK methods to define the fundamental PK properties of SL-401. Furthermore, if supported by the adequacy of the data, a population PK model will be developed, in which the effects of various potentially relevant co-variants (i.e., gender, age, IL-3R expression, immunogenicity) on relevant PK parameters, will be evaluated. Sample collection requires that the actual date and time (24-hour clock) that the SL-401 treatment begins (start of infusion, SOI) and ends (end of infusion, EOI) will be recorded as will be the date and time (24-hour clock time) of all blood samples.

Detailed instructions for collecting, processing, storing, and shipping the samples are provided in a separate procedure manual. [REDACTED]

Blood samples will be collected into ethylenediaminetetraacetic acid (EDTA) tubes (lavender top, at least 6 mL each); upon collection, the samples should be inverted gently several times to ensure adequate mixing of the EDTA anticoagulant and whole blood. Within approximately 30 minutes of collection, samples should be centrifuged in a refrigerated centrifuge to separate the plasma. An aliquot of the plasma (> 1 mL) will be transferred to a clean tube, tightly sealed, labelled appropriately and stored frozen at -70°C or below prior to analysis in the validated immunoassay.

Samples will be collected immediately prior to the start of the infusion of SL-401, immediately after end of infusion (time recorded), then 15, 30, 45, 60, 90, 120, 180, and 240 minutes after the completion of the infusion (see [Table 7](#)). It is recognized that it is not always possible to obtain the specimens at the precise time points specified above, although it is requested that sites make every effort to do so; it is essential that the precise time of infusion and times of subsequent PK sampling be recorded diligently).

The nominal blood sampling time schedule is summarized in [Table 7](#) for the following SL-401 treatment days:

- Cycles 1 and 3, infusion 1 (i.e., Day 1)
- Cycles 1 and 3, infusion 5 (i.e., usually Day 5)

8.13 Immunogenicity Studies

Peripheral blood samples (5 mL) will be collected (serum red top tube, no additive) for the detection and characterization of SL-401 reactive antibodies according to the schedule provided below.

- Cycle 1: Day 1 (pre-infusion), Day 15, and Day 28 (\pm 3 days)
- Cycle 2, 3, 4, 5, or 6: Day 1 (pre-infusion) and Day 28 (\pm 3 days). A separate Day 1 (pre-infusion) sample does not need to be drawn if the Day 28 sample from the prior cycle has been drawn no more than 24 hours prior to the first infusion of the next cycle to be given. In that case, the data for the Day 28 sample may be used both as the Day 28 sample for the prior infusion as well as the Day 1 (pre-infusion) sample, avoiding the necessity to draw 2 blood samples in close proximity.
- At least 16 to up to 20 weeks after the last SL-401 dose.
- If there are clinical manifestations suggesting either an infusion-related reaction or drug hypersensitivity, an immunogenicity sample should be obtained, as indicated in Section [7.5.5.2](#).

If infusions are held (postponed) for any reason, an immunogenicity sample must be collected within 3 ± 3 days after completion of the last SL-401 infusion for the cycle.

Samples for immunogenicity assessment will be evaluated by a central laboratory facility. Detailed instructions for collecting, processing, storing, and shipping the samples will be provided in a separate procedure manual.

In the setting of detection of SL-401 reactive antibodies, plasma from corresponding specimens may be evaluated for SL-401 levels (PK analysis). Plasma from patients without SL-401 reactive antibodies would then be utilized as a control for this PK analysis.

Following the required immunogenicity and PK evaluations, if additional serum or plasma is available, this serum and/or plasma may be used for evaluation of other relevant markers (for example IL-3 levels) if considered appropriate by the Sponsor or principle Investigator.

9 Schedule of Events

The study schedule of events is summarized in [Table 5](#), [Table 6](#), and [Table 7](#).

9.1 Study Day -14 to -4: Screening

The following evaluations will be performed on Study Day -14 to -4 to determine the patient's eligibility for the study and in anticipation of study drug:

- Informed consent
- Inclusion / Exclusion criteria
- Medical history, including prior therapy and concomitant medications
- ECOG PS
- Physical examination, including vision assessment
- Urine or serum pregnancy test
- Vital signs and weight
- 12-lead ECG
- ECHO or MUGA scan (within 28 days prior to start of first cycle of study drug)
- Clinical laboratory tests: hematology, serum electrolytes and chemistry (including albumin), coagulation parameters, and urinalysis
- Bone marrow aspiration (+ biopsy) within 14 days prior to start of first cycle of study drug.

Investigators will maintain a confidential log of all patients who have been screened for participation in the study whether or not the patient was eligible for study participation.

9.2 Study Day -1 to 0: Procedures Prior to Start of Treatment

- Concomitant medication assessment
- Physical examination
- Vital signs and weight
- 12-lead ECG
- Clinical laboratory tests: hematology, serum electrolytes and chemistry (including albumin)

9.3 Cycle 1

9.3.1 Study Days 1 – 5 (Up to Study Day 10 if Infusion(s) Held): Pre-Infusion

- Inpatient admission (Study Day 1) or treatment at a suitable outpatient facility
- Vital signs and weight
- AE and SAE monitoring
- Clinical laboratory tests: hematology, serum electrolytes and chemistry (including albumin), coagulation parameters, and urinalysis (Day 1 only for urinalysis)
- Collection of peripheral blood for immunogenicity (infusion 1) and PK sampling (infusions 1 and 5) immediately prior to the start of the infusion
- 12-lead ECG
- Diphenhydramine 50 mg IV 60 minutes prior to infusion
- Acetaminophen 650 mg PO 60 minutes prior to infusion
- Methylprednisolone 50 mg IV (or an equivalent dose of another corticosteroid) 60 minutes prior to infusion
- Ranitidine 50 mg IV (or an equivalent doses of another H₂-histamine antagonist) 60 minutes prior to infusion

9.3.2 Study Days 1 – 5 (Up to Study Day 10 if Infusion(s) Held): Infusion

- 12-lead ECG (infusions 1 and 5) performed at 3 distinct time points (triplicates) at pre-infusion and within 5 minutes prior to each PK sample collection at 30 and 60 minutes post-infusion
- Collection of peripheral blood for PK sampling (infusions 1 and 5) collected immediately after end of infusion (time recorded), then 15, 30, 45, 60, 90, 120, 180, and 240 minutes after the completion of the infusion
- 15-minute IV infusion of SL-401 at required dose
- Vital signs: immediately after completion of infusion and 30, 60, and 240 minutes post-infusion
- Monitoring for at least 4 hours
- AE and SAE monitoring

NOTE: For Cycle 1, SL-401 must be administered in the inpatient setting, with hospitalization beginning the day of the first infusion of SL-401 (or a prior day) and ending 24 hours after the last infusion of SL-401. Subsequent cycles of SL-401 can be administered in the inpatient setting or in a suitable outpatient ambulatory care setting that is equipped for intensive

monitoring of patients with hematopoietic malignancies undergoing treatment, per the discretion of the Investigator and institutional guidelines and capabilities. Patients will be monitored for at least 4 hours following the administration of each infusion of SL-401.

9.3.3 Study Day 8 ± 3 Days, or 3 ± 3 Days After Completion of Infusions if Infusion(s) Held

- Concomitant medication assessment
- Clinical laboratory tests: hematology, serum electrolytes and chemistry (including albumin), coagulation parameters, and urinalysis
- AE and SAE monitoring

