7. The patient has uncontrolled, clinically significant pulmonary disease (e.g., chronic obstructive pulmonary disease, pulmonary hypertension) that in the opinion of the Investigator would put the patient at significant risk for pulmonary complications during the study.
8. The patient has known active or suspected central nervous system (CNS) leukemia. If suspected, CNS leukemia should be ruled out with relevant imaging and/or examination of cerebrospinal fluid.
9. The patient has uncontrolled intercurrent illness including, but not limited to, uncontrolled infection, disseminated intravascular coagulation, or psychiatric illness/social situations that would limit compliance with study requirements.
10. The patient is pregnant or breast feeding.
11. The patient has known positive status for human immunodeficiency virus (HIV), active or chronic Hepatitis B or Hepatitis C.
12. The patient is oxygen-dependent.
13. The patient has any medical condition which in the opinion of the Investigator places the patient at an unacceptably high risk for toxicities.

Investigational Product, Dose, and Mode of Administration:

SL-401 is a novel protein comprised of recombinant human IL-3 genetically fused to truncated diphtheria toxin protein. SL-401 targets the IL-3R, which is over-expressed on the cancer stem cells (CSCs) and bulk of various leukemias and hematopoietic malignancies relative to normal hematopoietic stem cells and other hematopoietic cells.

A cycle of therapy is 28 days. SL-401 is provided as an IV injectable and administered as a 15-minute IV infusion for the first 5 consecutive days of a 28-day cycle. In Stage 1, the first cycle of SL-401 must be administered in the inpatient setting, with hospitalization beginning the day of the first infusion of SL-401 (or a prior day) and ending approximately 24 hours after the last infusion of SL-401. Subsequent cycles of SL-401 can be administered in the inpatient setting or in a suitable outpatient ambulatory care setting that is equipped for intensive monitoring of patients with hematopoietic malignancies undergoing treatment, per the discretion of the Investigator and institutional guidelines and capabilities. Patients will be monitored for at least 4 hours following the administration of each infusion of SL-401.

Patients with evidence of ongoing disease control during treatment (without evidence of clinically

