7.5.2 Dose, Schedule, and Duration of Treatment

Patients will receive SL-401 by IV infusion over 15 minutes for 5 consecutive days (or 5 doses over a period not to exceed 10 days if postponement is required for toxicity) of a 28-day cycle in the absence of disease progression or other withdrawal criteria.

Refer to the Pharmacy Manual for details regarding SL-401 administration.

Patients with evidence of ongoing disease control during treatment (without evidence of clinically significant progressive disease or intolerable toxicity) may receive repeated cycles of

SL-401 even if eradication of MRD, in the judgment of the Investigator, is not attained. Patients can receive up to 6 total cycles of SL-401 as long as there is ongoing evidence of AML remission, as determined by the Investigator. The administration of additional cycles of SL-401 (> 6 cycles) must be discussed with the Medical Monitor at which time the individual patient's potential risk/benefit of further treatment will be assessed.

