7.5.3 SL-401 Premedication and Dose Preparation and Administration

7.5.3.1 Premedication

Patients will receive the following premedication approximately 60 minutes before each SL-401 infusion:

- Acetaminophen 650 mg by mouth (PO)
- Diphenhydramine 50 mg IV
- Methylprednisolone 50 mg IV (or an equivalent dose of another corticosteroid)
- Ranitidine 50 mg IV (or an equivalent dosage of another H₂-histamine antagonist)

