7.5.3.3 Inpatient and Outpatient Setting for Dose Administration

In Stage 1, the first cycle of SL-401 must be administered in the inpatient setting, with hospitalization beginning the day of the first infusion of SL-401 (or a prior day) and ending approximately 24 hours after the last infusion of SL-401. Subsequent cycles of SL-401 can be administered in the inpatient setting or in a suitable outpatient ambulatory care setting that is equipped for intensive monitoring of patients with hematopoietic malignancies undergoing treatment, per the discretion of the Investigator and institutional guidelines and capabilities. Patients will be monitored for at least 4 hours following the administration of each SL-401 infusion.

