7.5.4 Patient Monitoring Procedures During the SL-401 Dosing Period

During each cycle, tests and procedures that may result in withholding of a scheduled SL-401 infusion, largely based on unresolved manifestations of fluid retention and/or other relevant acute toxicities during daily dosing, are described below and summarized in [Table 5](#) and [Table 6](#).

Vital Signs: Blood pressure, heart rate, respiration rate, body temperature, and pulse oximetry during dosing period (usually Days 1, 2, 3, 4 and 5): immediately prior to infusion, immediately

after completion of infusion, and 30, 60, and 240 minutes post-infusion; and Days 8, 15, 21 and 28.

Diagnostic Tests:

- During dosing period prior to SL-401 infusion (usually Days 1, 2, 3, 4, 5) and Days 8, 15, 21 and 28: Complete blood count (CBC) with differential, platelets, sodium, potassium, chloride, bicarbonate, blood urea nitrogen (BUN), creatinine, glucose, total protein, albumin, calcium, phosphorus, uric acid, total bilirubin, ALT, AST, alkaline phosphatase, lactate dehydrogenase (LDH), prothrombin time (PT) or International Normalized Ratio (INR), and activated partial thromboplastin time (aPTT)
- Days 1 (prior to SL-401 infusion), 8, 15, 21, and 28: routine urinalysis
- For temperature $\geq 38^{\circ}\text{C}$, draw blood culture $\times 2$, and collect urine for urinalysis and culture

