9.4.1 Days 1 – 5 (Up to Day 10 if Infusion(s) Held): Pre-Infusion

- Inpatient admission (Day 1) or treatment at a suitable outpatient facility
- Concomitant medications
- Vital signs and weight
- 12-lead ECG
- Clinical laboratory tests: hematology, serum electrolytes and chemistry (including albumin), coagulation parameters, and urinalysis (Day 1 only for urinalysis)
- Collection of peripheral blood for immunogenicity (infusion 1) immediately prior to the start of the infusion
- AE and SAE monitoring
- Diphenhydramine 50 mg IV 60 minutes prior to infusion
- Acetaminophen 650 mg PO 60 minutes prior to infusion
- Methylprednisolone 50 mg IV (or an equivalent dose of another corticosteroid) 60 minutes prior to infusion
- Ranitidine 50 mg IV (or an equivalent doses of another H₂-histamine antagonist) 60 minutes prior to infusion

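### Protocol 9.3.1 permits outpatient dosing in Cycle 1 without a stage limit, which for Stage 1 contradicts the inpatient requirement stated in three other places

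*Protocol*

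**What the plan says.** Four places in the protocol address where the first cycle is given.

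- **9.3.1 (Cycle 1, pre-infusion):** the first bullet reads "Inpatient admission (Study Day 1) or treatment at a suitable outpatient facility". It names no stage and sets no condition on the facility beyond suitability.
- **9.3.2 (Cycle 1, infusion), closing NOTE:** "For Cycle 1, SL-401 must be administered in the inpatient setting". It names no stage either. The stay runs from the day of the first infusion, or earlier, to 24 hours after the last.
- **7.5.3.3 (the section on treatment setting):** "In Stage 1, the first cycle of SL-401 must be administered in the inpatient setting". The stay is defined in the same way, ending approximately 24 hours after the last infusion.
- **Synopsis (investigational product, dose and mode of administration):** the same rule as 7.5.3.3, again limited to Stage 1.

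The NOTE, 7.5.3.3 and the synopsis offer outpatient dosing only for later cycles, and only at a site able to monitor these patients intensively. The matching bullet for Cycles 2 to 6, in 9.4.1, is "Inpatient admission (Day 1) or treatment at a suitable outpatient facility". There it agrees with the rest of the protocol.

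**The concern.** Section 9 is the visit-by-visit list that site staff work from, so the 9.3.1 bullet is an operative instruction. A site that followed it could dose a Stage 1 patient as an outpatient in Cycle 1, against an explicit safety rule.

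Capillary leak syndrome (CLS) gives the rule its purpose. Protocol 7.5.5.1 says it may occur 3 to 8 days after treatment starts. Section 3.6.3 calls it the principal dose-limiting toxicity of Study 50047. Section 3.6.2 reports it as a serious event in 2 of 26 patients with BPDCN in Study STML-401-0114.

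The stake is narrower than a loss of all monitoring. Vital signs, weight, chemistry and albumin before each dose, and observation for at least 4 hours after it, apply in either setting (7.5.4, 7.5.5.1.3, 9.3.1, 9.3.2). The inpatient rule adds presence in hospital between doses and for about a day after the last.

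**Working it through.** **Step 1: compare the four places by stage.**

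| Place | Stage 1, Cycle 1 | Stage 2, Cycle 1 |
|---|---|---|
| 9.3.1 bullet | either setting | either setting |
| 9.3.2 NOTE | inpatient | inpatient |
| 7.5.3.3 | inpatient | no rule stated |
| Synopsis | inpatient | no rule stated |

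In the Stage 1 column, three mandatory statements stand against one bullet and nothing reconciles them. The intended rule is clear and the bullet is the wrong text.

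In the Stage 2 column, one statement stands against one. Two readings fit. The NOTE may lack the words *In Stage 1*, in which case either setting is allowed in Stage 2. Or the bullet may have been carried over from 9.4.1, in which case Stage 2 Cycle 1 is inpatient. The documents do not say which.

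**Step 2: how much hospital time depends on the rule.** The plan states no figure to reproduce. The inputs are:

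- infusion of 0.25 h, five daily doses (7.5.2: "Patients will receive SL-401 by IV infusion over 15 minutes for 5 consecutive days");
- five doses spread over at most 10 days if postponed for toxicity (7.5.2);
- stay ending about 24 h after the last infusion (7.5.3.3, NOTE);
- observation of at least 4 h after each infusion (7.5.3.3);
- premedication about 1 h before each infusion (7.5.3.1).

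Let L be the day of the last infusion, with infusions given at the same time each day. From the start of the first infusion, the required stay is (L − 1) × 24 + 0.25 + 24 hours.

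- No infusion held, L = 5: 96 + 0.25 + 24 = 120.25 h, about 5 days.
- Holds to the limit, L = 10: 216 + 0.25 + 24 = 240.25 h, about 10 days.

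From the same starting point, the minimum outpatient attendance for five doses is 5 × (0.25 + 4) + 4 × 1 = 25.25 h. Premedication is counted for doses 2 to 5 only. The difference is at most 120.25 − 25.25 = 95 h with no holds, and at most 240.25 − 25.25 = 215 h with dosing to Day 10. The second figure is an upper bound, because visits on held days, such as those for daily albumin, are not counted.

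**Step 3: set the stay against the CLS window.** Three to 8 days after initiation can be read as Days 3 to 8 or as Days 4 to 9.

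- L = 5: the stay ends on Day 6. Dosing visits already cover Days 3 to 5 (or 4 to 5), the stay adds Day 6, and Days 7 to 8 (or 7 to 9) fall after discharge in either setting.
- L = 10: the stay ends on Day 11 and covers the whole window on either reading.

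The held-dose case matters because falling albumin, weight gain and signs of CLS are themselves reasons to hold an infusion (7.5.5.1.2 to 7.5.5.1.4). The stay can also be shorter: if dosing stops for the cycle, it ends about 24 h after the last dose actually given.

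**Step 4: patients.** SAP 3.1 gives 18 enrolled in Stage 1 and 9 in Stage 2 at database lock, 18 + 9 = 27. These are enrolment counts. Neither document says whether anyone was dosed as an outpatient in Cycle 1.

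**The case against.** The best reply is that Stage 1 is already settled. Section 9.3.1 is a checklist, 7.5.3.3 is the section written to govern the setting, and the NOTE repeats the rule one subsection after the bullet. A site would have to act on one line and overlook a mandatory statement close by. That stands as a reason to rank the point low. It does not make the bullet correct.

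A second reply concerns Stage 2. The limit to Stage 1 in 7.5.3.3 and the synopsis would serve no purpose if Stage 2 first cycles were also inpatient only. That argument has force, and it is why an inpatient rule for Stage 2 cannot be read out of the documents. It does not prove the opposite, because the NOTE is unrestricted and no text other than 9.3.1 offers outpatient dosing in a first cycle.

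Third, hours in hospital are not a measure of risk. This is accepted: the hours show only what the rule governs.

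A reader might infer that Cycle 1 patients were in fact sent home, that dose-limiting toxicities were missed, or that all 27 patients were exposed to the error. The documents support none of these. Dosing-day checks are the same in both settings, and nothing records outpatient dosing in Cycle 1.

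**Conclusion.** The contradiction is real and is a drafting error with safety relevance. For Stage 1 Cycle 1, the 9.3.1 bullet is wrong as written. For Stage 2 Cycle 1, the protocol contains two incompatible statements and no basis for choosing between them.

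The wording governs hospital presence of about 5 days when no infusion is held and up to about 10 days when dosing runs to Day 10. Both figures assume infusions at the same time of day and a stay ending 24 h after the last. No effect is shown on dose-limiting toxicity, MRD eradication, relapse-free or overall survival, error rates or any planned analysis. The number of patients affected is unknown and may be zero. The point is minor, and is worth correcting because the correction is simple.

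**What to change.** **Stage 1 Cycle 1:** remove the outpatient option from the 9.3.1 bullet.

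**Stage 2 Cycle 1:** the sponsor should state which rule was intended and align 9.3.1, the NOTE, 7.5.3.3 and the synopsis. There are two ways:

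- *Outpatient dosing allowed in Stage 2:* add *In Stage 1* to the NOTE, confine the 9.3.1 option to Stage 2, and attach the intensive-monitoring condition that the other sections place on outpatient sites. The Stage 1 limit in 7.5.3.3 and the synopsis then stays.
- *Inpatient for every first cycle:* delete the option from 9.3.1 entirely, and remove *In Stage 1* from 7.5.3.3 and the synopsis. Changing 9.3.1 alone would leave those two sections narrower than the NOTE.

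**Reporting:** enter any Stage 1 Cycle 1 outpatient dosing that can be identified in the violation listing planned in SAP 2.2. On the present text, the same conduct in Stage 2 cannot be called a violation.

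**Cost:** a few words in two or three places, and no new analysis. SAP 3.1 already reports enrolment at database lock, so the edit now mainly corrects the record. The documents do not say that care setting was captured on the eCRF, so finding cases may depend on source documents or monitoring records.
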